GABA and Glx Spectra Analysis GABA and Glx MRS will be analyzed using Gannet software implemented within MATLAB. Analysis will be conducted in two principal stages: 1) processing of raw time-domain data from the scanner into GABA-edited frequency-domain difference (DIFF) spectra with the following steps – line broadening, zerofill, fast Fourier transform, and extraction of water frequency; 2) Spectra fitting to quantify the edited GABA signals. To perform GABA J-difference editing two acquisitions will be acquired differing in the manipulation of the GABA spin system. Subsequent subtraction of the manipulated acquisitions will reveal GABA signals under the more prominent creatine (Cr) signal at 3 ppm. Next difference editing will be applied by subtracting the larger Cr signal to identify the smaller GABA signal. Next, Cr signal frequency-domain fitting will occur in the editing-OFF spectra. This will be conducted because the small GABA signal is susceptible to magnet instabilities including scanner drift and experimental quandaries such as subject movement. Quantification of GABA spectra will be obtained by applying a Gaussian model with linear baseline to the GABA signals in the DIFF spectra constrained within frequencies from 2.8 to 3.6 ppm, a Lorentzian model for the Cr signals in the OFF spectra constrained between 2.7 and 3.1 ppm, and a GaussianLorentzian model for the unsuppressed water spectrum constrained between 2.8 and 3.6 ppm. The resulting outputs include the integral ratio of GABA relative to Cr, GABA concentration relative

to water in institutional units (i.u.). Glx ratio will be derived from LCModel version 6.3-1 software using a simulated basis set, the jMRUI Amares algorithm in a similar method described by O’Gorman and colleagues [178]. Integration of the co-edited Glx signal at 3.75 ppm will be carried out using a linear fit to the baseline and the sum of two Lorentzians to fit the doublet peak. A regression and/or correlation analysis will be used to determine the relationship between changes in connectivity, MRS and behavioral metrics (clinical pain measures and hypnotizability). We will include regressors of non-interest for time between study visits, sex, and age.

Secondary Outcome Measure G:

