G.1. Using MRS, we will evaluate the L-DLPFC GABA concentrations before and after cTBS in a double-blinded sham-controlled design. The cartesian coordinate of the L-DLPFC cTBS target will be used for MRS voxel placement. As an internal control, right DLPFC MRS will be acquired for each subject to distinguish the laterality of the hypnosis effect.

Aim G.2. We will test whether changes in functional connectivity and behavioral measures of hypnotizability and hypnotic analgesia are associated with alterations in GABA MRS concentration.

Secondary Hypothesis G: *cTBS neuromodulation of L-DLPFC-dACC connectivity is mediated by inhibitory inter-neuronal cortical pathways measured by GABA MRS in the L-DLPFC. Neuromodulation induced by TMS has been shown to increase L-DLPFC-dACC connectivity, but the neurochemistry underlying these changes is unknown.*

MRS Analysis:

MRS analysis will be conducted identical to the Secondary Outcome Measure F. A subtraction of metabolic concentrations between pre- and post-TMS sessions will be used for subsequent correlation between changes in hypnotic analgesia and clinical pain measures. After completion of the study, unblinded data will be used to determine active versus sham changes in metabolic concentrations.

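### The water-reference fit for MRS (Secondary Outcomes F and G) repeats the GABA window of 2.8 to 3.6 ppm, so the water-referenced GABA value is not usable as written

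*Combined protocol and SAP*

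**What the plan says.** The GABA and Glx analysis under Secondary Outcome Measure F (protocol section 9.6.2) gives three fit ranges in one sentence:

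- GABA: "GABA signals in the DIFF spectra constrained within frequencies from 2.8 to 3.6 ppm"
- Creatine: "a Lorentzian model for the Cr signals in the OFF spectra constrained between 2.7 and 3.1 ppm"
- Water: "a GaussianLorentzian model for the unsuppressed water spectrum constrained between 2.8 and 3.6 ppm"

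Earlier in the same paragraph, the editing step is said to "reveal GABA signals under the more prominent creatine (Cr) signal at 3 ppm". Two GABA measures come out of these fits: "The resulting outputs include the integral ratio of GABA relative to Cr, GABA concentration relative" to water, in institutional units.

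For Secondary Outcome Measure G, the pre/post comparison around cTBS, the protocol adds only that "MRS analysis will be conducted identical to the Secondary Outcome Measure F". No other section gives a different water range or a water frequency. The separate SAP covers the HIP scores and the test of the blind, and does not mention MRS.

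**The concern.** Water and GABA are different signals, yet they are given the same fit range to the decimal. The paragraph itself says what lies in that range: creatine and GABA, near 3 ppm. The water reference is the denominator of one of the two listed GABA outputs. If its fit range does not contain the water peak, that denominator measures something other than water.

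The water-referenced value is one of the two routes to GABA for Outcome F (association with clinical pain). Through the cross-reference, it is also one of the two routes for Outcome G (change in L-DLPFC GABA after active or sham cTBS). An analyst who followed the text literally would get a number in institutional units that does not express GABA relative to tissue water.

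**Working it through.** The plan gives no computed figure to reproduce. The check compares the stated ranges and then asks how much of a water line could fall inside 2.8 to 3.6 ppm.

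**Inputs from the documents**
- GABA range 2.8 to 3.6 ppm; creatine range 2.7 to 3.1 ppm; water range 2.8 to 3.6 ppm (section 9.6.2).
- Creatine, with GABA under it, at 3 ppm (section 9.6.2).
- 3T scanner (section 3, Study Locations).

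**Assumptions, not in the documents**
- Water centre c between 4.6 and 4.8 ppm.
- Water line width (FWHM) between 0.05 and 0.2 ppm.
- 127.7 Hz per ppm at 3T.

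**Step 1: compare the ranges.** The water range overlaps the GABA range completely. The creatine range contains the stated 3 ppm signal, so the creatine fit is consistent with the text.

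**Step 2: distance from the window to the peak.** Distance = c − 3.6 ppm; in Hz, multiply by 127.7; in line widths, divide by FWHM.

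**Step 3: share of the water line inside the window.**
- Lorentzian, with g = FWHM/2: share = [atan((3.6 − c)/g) − atan((2.8 − c)/g)] / π.
- Gaussian, with s = FWHM/2.3548: share = Φ((3.6 − c)/s) − Φ((2.8 − c)/s).

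The least favourable case for this point is c = 4.6 and FWHM = 0.2, so g = 0.1. Then atan(−10) − atan(−18) = −1.4711 + 1.5153 = 0.0442, and 0.0442/π = 0.0141.

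| Water centre (ppm) | Distance to upper edge | Line widths away (FWHM 0.2 to 0.05) | Lorentzian share (FWHM 0.05 / 0.1 / 0.2) | Gaussian share |
|---|---|---|---|---|
| 4.6 | 1.00 ppm, 128 Hz | 5 to 20 | 0.35% / 0.71% / 1.41% | essentially 0 |
| 4.7 | 1.10 ppm, 140 Hz | 5.5 to 22 | 0.30% / 0.61% / 1.21% | essentially 0 |
| 4.8 | 1.20 ppm, 153 Hz | 6 to 24 | 0.27% / 0.53% / 1.06% | essentially 0 |

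**Step 4: what the fit would measure.** The peak is outside the window in every case. If the constraint limits the data used, only a tail is available. If it limits where the fitted peak may sit, the peak is not allowed to be where water is. The tail also depends on line width: at c = 4.7, going from 0.05 to 0.2 ppm raises the Lorentzian share from 0.30% to 1.21%, about fourfold (1.21/0.30 = 4.0), with no change in the amount of water. A pre/post difference built on that denominator could move with line width alone.

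**The case against.** The strongest reply is that this is a copying slip. The text names an established processing package, and its first stage includes extracting the water frequency, so the pipeline evidently expects to find water in the data. The software may well have fitted the right region whatever the protocol says. This is plausible, and nothing suggests that the sponsor meant to fit water near 3 ppm. But locating the water frequency in stage one does not change the fit range stated for stage two, and the stated range is the only specification of that step.

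It is also fair to say that the water position and line width come from outside the documents. They are treated here as assumptions with a range, and the conclusion is the same across it.

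A reader might infer more than the documents support, in four ways:

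- **That the water-referenced value is undefined.** This is too strong. A Lorentzian line leaves about 0.3% to 1.4% of its area in the window. The value is not usable, but it is not mathematically undefined.
- **That Outcomes F and G are lost.** They are not. GABA relative to creatine is listed first among the outputs and can still be derived, and Hypotheses F and G name no reference.
- **That GABA/water ought to rank above GABA/creatine.** The plan lists both without ranking them. Preferring one would be a reviewer's choice, not a correction of an error.
- **That the Glx text sets out conflicting methods.** One sentence says "Glx ratio will be derived from LCModel version 6.3-1 software using a simulated basis set, the jMRUI Amares algorithm" and a later one says "Integration of the co-edited Glx signal at 3.75 ppm will be carried out using a linear fit to the baseline". The wording is unclear, but it defers to a cited source for the method, no numerical conflict is shown, and Hypotheses F and G concern GABA only.

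**Conclusion.** The point stands for the water fit range alone. As written, the rule gives no usable water reference, so the water-referenced GABA output for F, carried over to G, is not usable. The window's upper edge is 1.0 to 1.2 ppm (about 128 to 153 Hz) below the assumed water peak, and at most about 1.4% of the line's area lies inside it. This rests on water at 4.6 to 4.8 ppm and line widths of 0.05 to 0.2 ppm. The repeated range is visible in the protocol without either assumption.

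Severity is minor. GABA/creatine, the primary mechanistic outcome and the relevant clinical outcome are untouched. F and G are secondary, the MRS assessment in section 6.2.5 is headed optional, and section 9.7 puts the emphasis for secondary aims on effect size rather than significance. The documents do not show whether the written range was ever applied.

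**What to change.** In section 9.6.2, under the MRS analysis for Secondary Outcome Measure F, replace the water range with one that brackets the water resonance. Outcome G needs no separate edit because it refers back to F. Then check the processing settings. If the software already fitted the right region, only the text changes. If the written range was used, refit the stored spectra and recompute the water-referenced GABA values for F and G. The cost is one corrected range and, at most, a rerun on existing data; no new acquisition is needed.

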utilize a combined structural and functional targeting approach because the area of the L-DLPFC that is being targeted to modulate is the area that has the highest connectivity with the dACC. It has been demonstrated previously that such an approach can be applied within the L-DLPFC(58). Once the pre-TMS scan session is complete, the images will be exported to the Localite Neuronavigation System (93) so that while the participant is undergoing their motor threshold (MT) elicitation and the neuronavigation targeting is occurring such that the participant's target and dose will be completed in time for the rTMS (cTBS) session.

Stimulation Parameters: 80% of the resting motor threshold (rMT) was chosen as the dose of cTBS as this dose has been demonstrated to be optimal in suppressing the MEP. We will adjust the skull-prefrontal cortex distance to account for any differences in differential volume loss. We will utilize 800 pulses of continuous theta-burst (cTBS) with 30 Hz bursts at 6Hz as this has been demonstrated to be optimal in suppressing the MEP(82). We will apply two stimulation trains of 800 pulses with a 15-minute space in between each train of cTBS as has been previously described(27, 30). This stimulation session will be performed in between the pre- and post- TMS scanner sessions for both scanner session days (total of two stimulation sessions for each participant). The participant will receive cTBS stimulation in the manner described in the manual that is attached to the appendix of this protocol. The handle of the coil will be pointed backwards (45° angle to the sagittal line) and will be fixated in an arm. In order to preserve the blind, the participant will be randomized to the same rTMS (cTBS) condition for both scanner days(86).

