 - Resting State: This is the baseline scan required for the primary endpoint. Individuals with higher hypnotizability have been demonstrated to have higher functional connectivity between the dorsolateral prefrontal cortex and the dorsal anterior cingulate cortex (31).
 - Pain Induction: Using the same moderate thermal pain values identified above, functional brain responses to acute pain, will be measured following hypnosis (Hypnotic Analgesia) and non-hypnosis (Non-Hypnotic Analgesia) audio instructions. Randomization of hypnosis and non-hypnosis scan order for each participant will be kept consistent between both pre- and post-rTMS scans. Hypnotic analgesia during pain induction has been demonstrated to be instruction specific (38, 44) and produce alterations in functional connectivity (123).

MR Spectroscopy Assessment (Optional)

Imaging Procedure

- Structural Acquisition (T1/T2/DWI): A structural scan will be acquired for imaging analysis.
- 1H-MRS Spectroscopy: MEGA-PRESS (GABA/Glx) and NFL-PRESS (Broad spectra) spectroscopy sequences will be acquired bilaterally within the left and right DLPFC using a cutting-edge automated voxel placement procedure that precisely targets the identified connectivity coordinates.
- Resting State fMRI: A BOLD fMRI acquisition will be acquired while the participant is at rest to assess functional connectivity between the insula and DLPFC (bilaterally)

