Analyses will be restricted to the anterior cingulate, L-DLPFC, insular, and somatosensory cortices. The correlation in the active rTMS + HA condition is expected to be stronger than the correlation obtained in the sham rTMS + HA. To determine if a given rTMS condition is specifically associated with HA induced change in that stimulated L-DLPFC activity, a mask restricted to dACC, DLPFC, insula and somatosensory cortex will be utilized to extract the fMRI activity data. Regression analysis will determine the strength of the relationship between the reductions of fMRI activity within the hypnotic analgesia network(4, 19) during the active versus sham rTMS conditions. Regression analysis will be used to investigate whether greater activity and connectivity will be present in the HA network (anterior cingulate, L-DLPFC, insular, and somatosensory cortices) for active rTMS-augmented hypnotic analgesia versus hypnotic analgesia alone (sham rTMS).

Secondary Outcome Measure F:

F.1. To evaluate cortical excitatory and inhibitory neurotransmitters, 1H-MRS will be acquired to determine the concentrations of GABA and glutamate/glutamine (Glx).

F.2. We will evaluate the associations between neurotransmitter levels and functional connectivity as well as behavioral measures of clinical pain level and duration.

F.3. As an exploratory aim, we will acquire a broad spectra MRS scan to determine dysregulation in other neurometabolites, particularly myo-inositol - a marker of neuroinflammation linked to glial reactivity.

Secondary Hypothesis F: *L-DLPFC GABA levels will be negatively associated with clinical pain measures in participants with FMS.*

MRS Analysis:

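### No tissue correction is stated for the GABA voxel, so water-referenced GABA can give an attenuated or a negatively biased association in Secondary Hypothesis F, and the plan does not say which GABA output tests F

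*Combined protocol and SAP*

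**What the plan says.** The hypothesis in protocol section 9.6.2 is directional and between persons: "L-DLPFC GABA levels will be negatively associated with clinical pain measures in participants with FMS". Outcome F.2 relates neurotransmitter levels to clinical pain level and duration.

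The processing has two main stages. The first turns raw data into edited spectra; the second is "2) Spectra fitting to quantify the edited GABA signals". On outputs the text reads "The resulting outputs include the integral ratio of GABA relative to Cr" and then adds GABA concentration relative to water in institutional units. Neither is described as tissue-corrected, and neither is named as the measure for F.

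On the model: "A regression and/or correlation analysis will be used to determine the relationship between changes in connectivity, MRS and behavioral metrics". On covariates: "We will include regressors of non-interest for time between study visits, sex, and age". The analysis for Secondary Outcome G is stated to be identical.

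The voxel is placed by automated coordinates at each participant's own DLPFC cluster with the strongest connectivity to the dACC (section 9.1, Objective F; section 9.6.2, Outcome G.1). Inclusion criteria allow ages 18-70 (section 4.1).

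Structural images are available. Section 6.2.2 lists a T1 in the baseline targeting session, which also includes spectroscopy. Section 6.2.5 says of the optional MRS assessment: "Structural Acquisition (T1/T2/DWI): A structural scan will be acquired for imaging analysis". No section says these images will be used to obtain voxel tissue fractions.

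**The concern.** CSF contributes water signal but almost no GABA, and grey matter is taken to hold more GABA than white matter. Two people with identical tissue GABA can therefore have different water-referenced values because their voxels hold different tissue. Automated placement fixes the coordinate, not the tissue mix, and an individual connectivity peak lets that mix differ between people.

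This matters because F rests on a between-person correlation with a predicted sign. Tissue variation unrelated to pain is noise and shrinks the correlation. CSF that rises with pain severity or duration, beyond age and sex, lowers measured GABA in those with more pain and imitates the predicted result. Section 9.7 puts the magnitude of effects ahead of significance for secondary aims, so the size of r is itself what F delivers. Without tissue fractions the reader cannot tell which distortion occurred.

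**Working it through.** The documents give no sample size, power or effect size for F, so there is no planned figure to reproduce.

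**Inputs from the documents:** two-sided 0.05 and a usable sample of 80 (section 9.2). The 80 is for the primary outcome and is borrowed here.

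**Inputs assumed:** voxel CSF c with mean 0.10, SD 0.04; grey share of tissue s with mean 0.45, SD 0.05; white/grey GABA ratio 0.5; white/grey Cr ratio 0.9; water content 0.8 grey, 0.7 white, 1.0 CSF; true GABA CV 8%, 10% or 15%. SDs and correlations are read as those left after age and sex.

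**Water-referenced GABA.** Measured value = true GABA x T, with T = G/W.
- G = grey + 0.5 x white = (1 - c)(0.5 + 0.5s)
- W = c + (1 - c)(0.7 + 0.1s) = 0.7705 at the means
- Relative change in T per unit c: -1/0.90 - 0.255/0.7705 = -1.111 - 0.331 = -1.442; times 0.04 = 5.77%.
- Relative change in T per unit s: 0.5/0.725 - 0.09/0.7705 = 0.690 - 0.117 = 0.573; times 0.05 = 2.86%.
- Tissue CV = sqrt(5.77² + 2.86²) = 6.44%.

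*Tissue unrelated to pain.* Observed r = true r x CV/sqrt(CV² + 6.44²). At CV 10%: -0.30 x 10/11.9 = -0.25 (-0.23 at CV 8%, -0.28 at CV 15%). Simulation gives -0.25, with power 0.63 against 0.77 when corrected.

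*No true association, CSF-pain correlation 0.3.* Spurious r = -0.3 x 5.77/sqrt(CV² + 6.44²). Probability of a significant negative result by Fisher z: Phi(atanh|r| x sqrt(77) - 1.96).

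| True CV | Spurious r | Significant negative, n=80 |
|---|---|---|
| 8% | -0.17 | 32% |
| 10% | -0.15 | 25% |
| 15% | -0.11 | 15% |

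Simulation gives 16-32%; nominal is 2.5%.

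*True -0.30 and CSF-pain correlation 0.3 together* (CV 10%): -0.25 - 0.15 = -0.40 (simulated -0.39). The real association is inflated.

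**GABA/Cr.** The factor (1 - c) appears in numerator and denominator and cancels. What remains is the grey/white term: (0.5/0.725 - 0.1/0.945) x 0.05 = 2.9%. A true -0.30 becomes -0.30 x 10/sqrt(100 + 2.9²) = -0.29, and false significant negatives stay at about 3%.

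**Sensitivity.** A second simulation put age and sex in the model, added measurement error and used a wider CSF spread. For GABA/water at n=80 and a pain-volume-loss correlation of 0.3 it gave 23-29% significant negatives (8-34% as the SD of volume loss ran from 0.02 to 0.08). At n=40 the main scenarios gave 13-17%. With no pain-tissue link the rate stayed nominal. GABA/Cr gave 2-7%.

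**Candidate corrections.** Dividing only by grey + 0.5 x white leaves 1/W uncorrected: the residual CSF effect is 0.331 x 0.04 = 1.3%, a spurious r of -0.03 to -0.05, with 5-7% significant negatives in simulation. Grey and CSF fractions as regressors bring the rate to 2.6-2.8%.

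**The case against.** The best defence has four parts.

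- **The text is not closed.** It speaks of main stages and of what the outputs include, and structural images are acquired for imaging analysis. A reader might infer that GABA will certainly be analysed uncorrected. The documents support only that no correction is stated. In a description detailed enough to give fit models and ppm ranges, that is still a gap to fill.
- **GABA/Cr is a planned output, listed first, and is nearly immune to CSF.** This stands, and it confines the main concern to water-referenced GABA. It does not settle the matter, because neither output is assigned to F.
- **The false-positive route needs a CSF-pain link beyond age and sex.** The documents give no figure for one. A reader might take section 3 as support: "We will adjust the skull-prefrontal cortex distance to account for any differences in differential volume loss". That sentence concerns the stimulation dose; it neither reports volume loss in this sample nor ties it to pain. The attenuation route needs no such link.
- **The stakes are limited.** F is secondary, the MRS assessment in section 6.2.5 is optional, no MRS sample size is given, and section 9.7 does not rest secondary aims on significance. All true. The distortion of r remains.

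A reader might also infer that tissue mix creates a false association and weakens real ones at the same time. It does not: weakening occurs when tissue is unrelated to pain, whereas CSF that rises with pain inflates a true negative association.

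**Conclusion.** The concern holds in a limited form. As written, the plan leaves the water-referenced test of F open to attenuation, or to bias in the predicted direction, depending on whether voxel tissue tracks pain. The size is moderate: about 0.05 off a true r of -0.30 in the first case, and a spurious r of -0.11 to -0.17 at a CSF-pain correlation of 0.3 in the second. Every tissue value, that correlation and n=80 are assumptions.

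GABA/Cr carries only a small grey/white attenuation, so the unnamed choice between the two outputs is part of the problem. In Outcome G the left-right comparison is exposed in the same way. The within-person pre-post change is little affected if the voxel is placed identically. The primary outcome is untouched. This should be corrected, but the trial does not depend on it.

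**What to change.** In the MRS analysis of section 9.6.2:

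1. Co-register each MRS voxel to the T1 already acquired and segment it into grey matter, white matter and CSF.
2. For water-referenced GABA, add the voxel grey-matter and CSF fractions to the existing covariates. Alternatively, use a tissue-corrected value that also models the water signal of each tissue, with its constants fixed in advance; division by grey plus a weighted white fraction alone is not enough.
3. For GABA/Cr, add grey/(grey + white) as a regressor.
4. Name in advance the one GABA measure that tests F, and make the other a sensitivity analysis.
5. Apply the same treatment to the left-right comparison in G, and state that pre and post voxels are placed identically.

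The cost is a segmentation step, a few sentences in the plan and one or two degrees of freedom. No new scans or participant burden are needed.

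### The model stated for the Secondary G associations has no term for randomised arm, so a joint cTBS effect on GABA and outcome can produce a correlation with no within-arm link

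*Combined protocol and SAP*

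**What the plan says.** All references are to the combined protocol and SAP unless stated.

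- **Hypothesis G (section 9.6.2)** is a mediation statement: "cTBS neuromodulation of L-DLPFC-dACC connectivity is mediated by inhibitory inter-neuronal cortical pathways measured by GABA MRS in the L-DLPFC".
- **Aim G.2 (section 9.6.2)** is worded as an association: "We will test whether changes in functional connectivity and behavioral measures of hypnotizability and hypnotic analgesia are associated with alterations in GABA MRS concentration".
- **G's analysis text** first refers back: "MRS analysis will be conducted identical to the Secondary Outcome Measure F". It then says that the pre/post difference in metabolites "will be used for subsequent correlation between changes in hypnotic analgesia and clinical pain measures".
- **The analysis text for F** gives the model: "A regression and/or correlation analysis will be used to determine the relationship between changes in connectivity, MRS and behavioral metrics". It gives the covariates too: "We will include regressors of non-interest for time between study visits, sex, and age".
- **Arm** enters G's analysis text once, in a different sentence and for a different purpose: "After completion of the study, unblinded data will be used to determine active versus sham changes in metabolic concentrations".
- **Section 9.7** plans to look at mediators of the rTMS effect in general, by the MacArthur approach and by causal mediation methods. It mentions neither GABA nor Secondary G. The one mediation question spelled out in section 9.1 has connectivity change as the mediator and hypnotizability as the outcome.
- **The separate SAP (January 2024)** covers the HIP scores and the test of the blind, and says nothing about spectroscopy.

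**The concern.** Hypothesis F asks whether GABA levels go with clinical pain in people with fibromyalgia. That question needs no arm term. G borrows the same method for a before/after question in a randomised comparison, where arm can move both variables.

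When two change scores are correlated across both arms without an arm term, the coefficient has two parts: the association between participants within an arm, and the product of the two arm differences. The second part is non-zero whenever cTBS shifts both variables, even if participants with a larger GABA change have no larger outcome change than others in their arm. Two parallel effects of stimulation then look like a GABA-outcome link. If the arm effects have opposite signs, a true positive within-arm link is reduced or hidden.

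Hypothesis G itself supposes that cTBS changes both GABA and connectivity, so the distortion arises in the situation the protocol expects. At stake is the interpretation of a reported GABA correlation. The primary and clinical outcomes are not touched.

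**Working it through.** The documents give no sample size, power or correlation for Secondary G, so there is no stated figure to reproduce. The check is of the mechanism and its size.

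**Inputs**
- Arm effect on connectivity change: d = 0.8, the planning value in section 9.2, which cites 0.69 from one prior study.
- Arm effect on GABA change: not in the documents. Assumed, and varied from 0 to 1.2.
- Allocation 1:1, with 80 usable participants (40 per arm, section 9.2). This is the primary imaging sample. Section 6.2.5 marks the spectroscopy assessment as optional, so the spectroscopy sample may be smaller; 40 in total is used as an illustration.
- Two-sided 5% level, stated in section 9.2 for the power estimate and used here for illustration.
- Within-arm correlation: zero.

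**Formula.** Let each change score have within-arm SD 1 and arm differences d1 (GABA) and d2 (outcome), with within-arm correlation ρ. At 1:1 allocation the arm indicator has variance 0.25, so across both arms

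r = (ρ + 0.25·d1·d2) / √[(1 + 0.25·d1²)(1 + 0.25·d2²)]

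**Numbers with ρ = 0**
- d1 = d2 = 0.8: r = 0.16 / 1.16 = 0.138, so r² is about 0.019.
- d1 = 0.5, d2 = 0.8: r = 0.10 / √(1.0625 × 1.16) = 0.10 / 1.110 = 0.090.
- d1 = 0: r = 0.

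r does not depend on the sample size, so a larger sample does not shrink it.

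**Opposite signs.** With d1 = −0.8 and d2 = 0.8, the numerator is ρ − 0.16. A within-arm correlation of 0.16 would be cancelled exactly.

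**Rejection rates**, from 20,000 simulated trials per row and sample size, ρ = 0:

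| d on GABA | d on outcome | r | No arm term, N=40 | No arm term, N=80 | With arm term, N=80 |
|---|---|---|---|---|---|
| 0 | 0.8 | 0 | 4.8% | 5.1% | 5.2% |
| 0.4 | 0.4 | 0.038 | 5.6% | 6.2% | 5.0% |
| 0.5 | 0.8 | 0.090 | 8.8% | 12.1% | 5.1% |
| 0.69 | 0.69 | 0.106 | 9.9% | 15.5% | 5.2% |
| 0.8 | 0.8 | 0.138 | 13.7% | 23.1% | 5.0% |
| 1.2 | 1.2 | 0.265 | 39.6% | 68.7% | 5.0% |

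With an arm term the mean correlation was about zero, and rejection stayed between 4.6% and 5.3% in every scenario run. The last row lies beyond the protocol's planning value and only shows the direction of travel.

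**The case against.** **Pooling is not stated.** A reader might infer that the plan says the arms are pooled. It does not: G's text is silent on pooling, stratification and adjustment. The covariate list is of nuisance variables, so the factor of interest need not appear there, and the reference back to F may be mainly about spectral processing. This stands in part, and the point is therefore about the model as stated. But F's text also contains the association model, and arm is not in it. For the primary outcome and for Secondary A, C, D and E, section 9.6 contrasts the correlation in the active arm with that in sham. F and G have no such wording.

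**Section 9.7 may already cover this.** Hypothesis G concerns a mediator of the rTMS effect, and the methods in 9.7 include treatment by construction. This stands to the extent that a reader should not infer that the whole plan rests mediation on an unadjusted correlation. What is missing is the assignment of GABA and Hypothesis G to those methods.

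**The sentence on the correlation concerns analgesia and pain, not connectivity.** Correct. The connectivity link comes from Aim G.2 and from F's model. Nor do the documents say that the correlation will be offered as proof of mediation, so a reader should not infer that a false mediation claim is planned.

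**The size is modest and rests on an assumed GABA effect.** Also correct. Section 9.7 puts the weight for secondary aims on effect size, not significance, and 0.138 is about 2% of variance. That does not remove the point, because the spurious r is itself a biased effect size.

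**An arm term does not identify mediation.** This stands in full, since GABA change is not randomised.

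**Conclusion.** The concern holds as a gap in the stated model. Followed as written, the Secondary G associations carry no arm term, and arm is used only for a separate comparison of metabolite change. If cTBS shifts both GABA and the outcome, the reported association is non-zero without any within-arm link.

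At d = 0.8 on both, the bias is r of about 0.14, with about 23% rejection at 80 participants and 14% at 40. With 0.5 on GABA and 0.8 on connectivity, the rate is about 12% at 80. With no GABA effect, there is no artefact. These figures assume 1:1 allocation, zero within-arm correlation and a GABA effect that the documents do not supply.

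The documents do not support the stronger conclusion that the trial will report GABA mediation that does not exist. The issue is confined to one optional secondary aim. It is worth correcting because the distortion arises where Hypothesis G expects an effect, and the correction uses data the trial already holds.

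**What to change.** 1. Run the G association models after unblinding, with the outcome change regressed on arm, GABA change, visit interval, sex and age. Report the arm-adjusted (within-arm) association as the result.
2. Treat arm × GABA change as exploratory only, because the optional spectroscopy sample may be small and the interaction imprecise.
3. State that the mediation methods in section 9.7 apply to Hypothesis G, with arm as exposure, change in L-DLPFC GABA as mediator and change in L-DLPFC-dACC connectivity as outcome. State their assumption of no unmeasured mediator-outcome confounding, since GABA change is not randomised.
4. Do not present an association without arm adjustment as evidence of mediation.

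The cost is SAP wording and one model term, with slightly less precision than a pooled estimate. No new data, visits or participants are needed.
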